13. STATISTICAL CONSIDERATION

13.1 Sample Size

This study is a Simon (minimax) two-stage design that will enroll up to a total of 39 subjects. The primary endpoint is overall disease control. In the first stage, a total of 28 subjects in the evaluable population will be enrolled. Of these, if at least 8 should

achieve disease control (Section 13.1.1) the study will continue on to the second stage. In the second stage, 11 participants in the evaluable population (total of 39) will be enrolled. If at least 16 of the 39 total subjects enrolled achieve disease control then we will be able to reject the null hypothesis. The sample size of evaluable population for both Stage 1 and Stage 2 include participants who begin nintedanib therapy.

Given the lack of information of clear benefit of any therapy in the second line setting of subjects with appendiceal carcinoma, a disease control rate of 30% would be considered an inferred clinical historical rate. Alternatively, a 50% disease control rate which, if achieved, would be worthy of further investigation. Assuming a one-sided $\alpha = 0.10$ significance level, this design will provide at least 90% power to reject the null hypothesis, assuming the true disease control rate is 50%.

Endpoint Definitions

13.1.1. Disease Control

Disease control will be determined for each subject as a binary variable indicating whether or not subjects with measurable disease achieve a best overall response of CR, PR, or SD as determined by RECIST 1.1 and subjects with non-measurable disease have at least one evaluable disease assessment indicating non-progressive disease.

13.1.2. Objective Response

Objective response will be determined for each subject as a binary variable indicating whether or not the subject achieved a best overall response of CR or PR as determined by RECIST 1.1.

13.1.3. Progression-Free Survival

Progression-free survival (PFS) is defined as the duration of time from the start of nintedanib treatment to first occurrence of either progressive disease or death. Disease progression can be objectively determined as per Section 12 (RECIST 1.1) or progression can be subjective as determined by the investigator. Evidence for subjective progression must be documented in the medical records. For objective disease progression, the date of PD is the date of the radiologic assessment that identified RECIST-defined progressive disease. For subjective disease progression, the date of PD is the date that the clinician makes the determination of disease progression. If the subject died without documented disease progression, the date of progression will be the

date of death. For surviving subjects who do not have documented disease progression, PFS will be censored at the date of last radiologic assessment. For subjects who receive subsequent anti-cancer therapy prior to documented disease progression, PFS will be censored at the date of last radiologic assessment prior to the commencement of subsequent therapy. Subjects who have an initial PFS event immediately following 2 or more consecutive missed assessments will be censored at the date of the last assessment prior to those missed assessments. For subjects with only one missed assessment, the documented progressive disease status and assessment date will be used.

13.1.4. Six-Month Progression-Free Survival

Six-month progression-free survival will be determined for each subject as a binary variable indicating whether or not the subject is alive and progression free at 6 months. The criteria for a PFS event are defined in Section 13.1.3.

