Specimens will be collected according to the schedule in Section 6. Specimens will be collected after subject eligibility confirmation, but prior to administration of the first dose of nintedanib and subsequent cycles. Exploratory biomarker arrays may be used.

Radiology and Tumor Measurements. A computed tomography (CT) scan with oral and intravenous contrast of the chest, abdomen and pelvis will be performed within 28 days prior to the first dose of nintedanib (screening scan). Scans will then be performed within 7 days following anticipated completion of cycle 2 unless clinically proven otherwise and within 7 days of anticipated completion of every two cycles thereafter (e.g. end of cycles 4, 6). A contrast-enhanced MRI of the abdomen and pelvis and a CT scan of the chest without contrast may be substituted if clinically necessary; however, subsequent studies must be performed using the same imaging modality throughout the study period.

For subjects who discontinue study therapy due to toxicity or reasons other than progressive disease, every effort will be made to obtain imaging studies and tumor assessments every 8 weeks (+/- 2 weeks) until documented progression or the start of subsequent anti-cancer therapy.

Subsequent Therapy and Survival Status. Once subjects complete their End of Treatment visit, they will be followed until all treatment-related toxicities have resolved, returned to baseline, stabilized, or are deemed irreversible. Subject's initial anti-cancer therapy following discontinuation of nintedanib treatment and survival

status will be documented.

Subjects (or their family members or designees) may be contacted by telephone, in writing, or during clinic visits after treatment discontinuation for collection of long-term follow-up data approximately every 6 months until death or lost to follow-up, or until the criteria defined for the final analysis (Section 13.3.1) are reached. However, in the event the criteria for the final analysis are met, and there are subjects who have not yet been discontinued from nintedanib treatment, subjects in follow up will continue to be followed until all subjects have discontinued study treatment and completed the safety monitoring period. Long-term follow-up clinical information may also be obtained through chart reviews.

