7. TREATMENT PLAN

7.1. Nintedanib Dosage and Administration

Research participants for this study will initiate treatment with 200mg of oral nintedanib twice per day. The capsules should be swallowed whole (unopened, uncrushed) with a glass of approximately 8 oz. /240 mL of water. Since subjects will be taking oral nintedanib twice daily, the dose interval should be every 12 hours at the same time every day, usually in the morning and the evening after food intake.

In case of a missed dose the subjects should not replace that dose, but proceed to the next scheduled dose when it is due. Each study cycle length is 28 days.

In the event of a treatment delay at the scheduled Day 1 of a cycle, Day 1 of that cycle will be delayed until study treatment is re-started. This may cause a cycle to extend to longer than 28 days. Day 1 will be defined as the day the treatment is re-started.

For dose selection and modifications, see Section 8.

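### Six-month PFS is a yes/no rate with an exact binomial interval, but subjects censored before 6 months have no scoring rule and 6 months is not defined in days; report the Kaplan-Meier estimate at one prespecified day

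*Combined protocol and SAP*

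**What the plan says.** Section 13.1.4 defines the endpoint as "a binary variable indicating whether or not the subject is alive and progression free at 6 months" and adds only that "The criteria for a PFS event are defined in Section 13.1.3". Section 13.3.4.2 and the Statistical Analysis row of the Protocol Summary give the rate a 95% Clopper-Pearson interval. Section 13.2 makes everyone who starts nintedanib the population. Section 13.3.4.2 also plans Kaplan-Meier estimates of PFS, without naming a time point.

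Section 13.1.3 has three censoring rules:
- Survivors without documented progression are censored at their last scan. This covers withdrawal and loss to follow-up.
- A subject who starts new therapy before progressing is also censored; the rule reads "PFS will be censored at the date of last radiologic assessment prior to the commencement of subsequent therapy".
- The third rule concerns gaps in scanning: "Subjects who have an initial PFS event immediately following 2 or more consecutive missed assessments will be censored"; the censoring date is that of the last scan before the gap.

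On treatment, section 5.5 schedules scans at the end of cycle 2 and "within 7 days of anticipated completion of every two cycles thereafter". For subjects who stop for reasons other than progression, scans every 8 weeks are sought "until documented progression or the start of subsequent anti-cancer therapy". Survival contact continues "approximately every 6 months until death or lost to follow-up". Section 7.1 says of a treatment delay: "This may cause a cycle to extend to longer than 28 days".

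**The concern.** A binomial proportion needs a yes or a no from every subject in its denominator. The plan's own PFS rules produce subjects who may have neither at 6 months. Someone who stops for toxicity and starts another drug in month 3 is no longer scanned under the protocol. Unless that person is known to have died, the 6-month status is unknown. Scoring such subjects as failures pulls the rate down and scoring them as progression-free pushes it up. Leaving them out departs from the all-treated population. Three analysts could each do one of these and claim to follow the plan.

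The missed-assessment rule adds a second ambiguity. A progression or death before 6 months that follows two missed scans is censored in the PFS analysis. Section 13.1.4 does not say whether it is a failure in the binary one.

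The undefined day matters even with complete follow-up. A subject whose last clear scan is on day 168 passes a 24-week landmark but is unresolved at day 183.

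At stake is how a named secondary endpoint is reported. The Kaplan-Meier curve and the binary rate could give two different 6-month figures from the same subjects, with the coding chosen after the data are seen in an open-label, single-arm trial.

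**Working it through.** **Plan's own figures.** The documents give no expected 6-month PFS rate, early-censoring rate or precision target, so there is nothing to reproduce for this endpoint. The primary design does reproduce. Summing P(X1 = x) × P(X2 ≥ 16 − x) over x ≥ 8, with X1 from 28 subjects and X2 from 11, gives type I error 0.0943 at 30% and power 0.9001 at 50%. Six-month PFS plays no part in it.

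**Effect of the coding (hypothetical data).** Take 39 treated subjects with 12, 6 and 4 events at days 56, 112 and 168, and 2, 1 and 1 censored just after those scans. That is 22 events, 4 censored and 13 known progression-free.

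| Handling of the 4 | Estimate | 95% CI |
|---|---|---|
| Failures | 13/39 = 33.3% | 19.1–50.2 |
| Excluded | 13/35 = 37.1% | 21.5–55.1 |
| Progression-free | 17/39 = 43.6% | 27.8–60.4 |
| Kaplan-Meier | 27/39 × 19/25 × 14/18 = 40.9% | 25.0–56.2 |

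Failure and success coding differ by 4/39 = 10.3 points whatever the model. If 6 months means day 168, the subject censored just after that scan is progression-free and failure coding gives 14/39 = 35.9%, not 33.3%.

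**Bias under continuous observation (assumed).** Exponential PFS with S(6 months) = 0.35, so L = −ln 0.35 = 1.0498, and independent exponential censoring with cumulative hazard m by 6 months. The unknown fraction is q = m/(m + L) × (1 − 0.35e^(−m)). The failure-coded rate is 0.35e^(−m), the success-coded rate adds q, and latent censoring is 1 − e^(−m).

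| q | m | Latent censoring | Failure coding | Success coding |
|---|---|---|---|---|
| 5% | 0.0836 | 8% | 32.2% | 37.2% |
| 10% | 0.1733 | 16% | 29.4% | 39.4% |
| 20% | 0.3753 | 31% | 24.0% | 44.0% |

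Kaplan-Meier targets 35% throughout. Failure coding is low by 2.8, 5.6 and 11.0 points.

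**On the plan's scan grid.** Simulated with scans at days 56, 112, 168 and 224, on the nominal day or up to 7 days late, and 0–50% of events dated exactly. Progression is found late on this grid, which pushes every estimate up. Failure coding gives 33.5–35.6%, 30.9–33.1% and 25.9–28.2% at 5%, 10% and 20% unknown. Kaplan-Meier read at day 183 gives about 34–38%. At its upper end, with every event found by an on-time scan, it estimates S(168) = 0.35^(168/183) = 38.1%. So at 5% unknown failure coding (largest error 1.5 points) is at least as good as Kaplan-Meier (about 3). At 10% the two are similar, with failure coding up to 4.1 low. At 20% Kaplan-Meier is clearly better, with failure coding 6.8–9.1 low.

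**Time point.** Six cycles of 28 days end on day 168; half a year is 365.25/2 = 182.6 days. Assume each start of cycles 2–6 is delayed with probability 0.2 by a uniform 3–14 days, and that the scan moves with the cycle. An on-time scan passes day 183 if total delay exceeds 15 days:
- two delays: 0.2048 × (1 − 81/242) = 0.136
- three delays: 0.0512 × (1 − 216/7986) = 0.050
- four or five delays: about 0.007

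The total is about 19%. If scans are also 0–7 days late, simulation gives 33%.

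**The case against.** The strongest reply is that the plan already implies an answer. Section 13.2 keeps every treated subject in the denominator, and section 13.1.4 asks whether the subject is alive and progression-free, so an unknown is naturally not a success. Failure coding is a recognised conservative convention. In the grid simulation its Clopper-Pearson interval still covers 95–97% at 10% unknown, falling to 83–90% only at 20%. If leaving doubles the hazard, failure coding at 10% unknown (32.9–34.1%) is closer to 35% than Kaplan-Meier (37.3–38.4%). Most of this stands. It makes failure coding defensible, but the plan does not state it, and it does not settle the day.

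The 20% case is also extreme. Section 13.3.1 triggers the final analysis when PFS censoring falls to 20%, or at 3 years. Under the first trigger nearly every censored subject would have had to leave before 6 months. The 3-year trigger allows more. That objection stands too.

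The unknown group is also kept small by end-of-treatment scans, off-treatment scans, clinical progression, and survival contact that identifies deaths. By the updated analysis everyone has a year on study, so administrative censoring is minor. Finally, the interval at 14/39 is 21.2–52.8%, a half-width of about 16 points, wider than any difference between Kaplan-Meier and failure coding shown here.

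**Conclusion.** The point holds as a modest improvement to a secondary endpoint. The plan applies a binomial method to an outcome that its own rules can leave unknown, gives no scoring rule, and does not fix the day. The Kaplan-Meier estimate that it already plans handles the censoring directly. The gain is small at 5–10% unknown and material only near 20%. All sizes rest on an assumed true rate of 35%, exponential times and, in the main figures, independent censoring.

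The documents do not support four stronger inferences that a reader might draw:
- **That the planned rate is necessarily biased.** They do not say how unknowns will be coded or how many there will be.
- **That Kaplan-Meier is unbiased here.** New therapy after a toxicity stop may be informative, and scan timing alone can move the estimate by about 3 points.
- **That a third of end-of-cycle-6 scans will fall after day 183.** The 19–33% range needs the assumed delays. It also needs the scan to move with the cycle, which section 5.5, tied to anticipated completion, does not say.
- **That the trial's decision is at risk.** The 28/39 rule uses disease control only.

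**What to change.** In sections 13.1.4 and 13.3.4.2, and in the Protocol Summary row:

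1. Define 6 months as one day counted from the first dose, with a scan window tied to the end-of-cycle-6 assessment, and say whether that scan follows a delayed cycle. The day sets what is estimated: under the model above PFS is 35% at day 183 but 0.35^(196/183) = 32.5% at day 196, so a later reading must not be labelled as the earlier one.
2. Make the Kaplan-Meier PFS estimate at that day, with a 95% log-log (Greenwood) interval in all treated subjects, the reported 6-month PFS rate. Keep Clopper-Pearson for disease control and objective response.
3. Keep the binary rate with its Clopper-Pearson interval as a sensitivity analysis in all treated subjects at the same day. Any death or progression by that day is a failure, including a death after new therapy, and unknown status is a failure. Date progression first seen in the window as in the main analysis.
4. State whether the missed-assessment rule in section 13.1.3 applies to the 6-month rate, including to deaths.

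The cost is a few sentences: same data, a method already in the plan, no added scans or visits. The downside is that Kaplan-Meier assumes non-informative censoring, so it should be read beside the sensitivity analysis.

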13.1.5. Overall Survival

Overall survival is defined as the duration from the start of nintedanib treatment to the date of death from any cause. Subjects who are alive or lost to follow-up at the time of the analysis will be censored at the last known date they were alive.

13.1.6. Safety Endpoints

Safety endpoints will include treatment administration, AEs, SAEs, deaths while on study therapy, and blood pressure. Treatment administration will be determined for each subject in terms of cumulative and average daily dose of nintedanib administration (adjusting for dose delays and reductions). Additionally, the relative dose intensity will be calculated for each subject in terms of the actual daily dose administered as a percent of the intended daily dose.

13.2. Analysis Populations

The response-evaluable population for the analysis of objective response will include enrolled subjects with measurable disease at baseline. The evaluable population for the analysis of disease control, all other secondary endpoints, and safety endpoints will include subjects who begin nintedanib treatment. The sample size requirements for

Stage 1 and 2 described above pertain to the evaluable population for the analysis of disease control.

13.3. Analysis Methods

13.3.1. Timing of Analysis

The Stage 1 analysis will be conducted after the best overall response for all Stage 1 evaluable subjects has been determined. The primary analysis of Stage 2 will be conducted after the best overall response of all evaluable subjects has been determined. An updated analysis will be conducted after all enrolled participants have been on study for at least one year. The final analysis will be conducted after the PFS censoring rate reduces to 20% or after all subjects have been on study for at least 3 years, whichever occurs first.

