5.4.2. Subject Withdrawal

Subjects are defined as withdrawn from the study if they revoke consent for both treatment and study procedures or the Investigator withdraws them from the study. Subjects **must be** withdrawn from the trial for any of the following reasons:

- Subject withdraws consent from study treatment and study procedures. A subject must be removed from the trial at his/her own request. At any time during the trial and without giving reasons, a subject may decline to participate further. The subject will not suffer any disadvantage as a result.
- Subject is lost to follow-up after three consecutive unsuccessful documented attempts at contacting the subject.
- Development of an intercurrent illness or situation which would, in the judgment of the Investigator, significantly affect assessments of clinical status and trial endpoints.

Subjects may be completely withdrawn from the study by the Investigator if criteria for long-term follow-up described in Section 5.5 are met.

Any subject who withdraws themselves or who is withdrawn from the study by the Investigator will remain under medical supervision until discharge or transfer is medically acceptable.

In all cases, the reason for withdrawal must be documented in the subject's medical records and/or research chart and recorded in the CTMS. Withdrawn subjects are considered to be off-study. Details for the premature termination of the study as a whole are provided in Section 14.2.

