7.3. Duration of Therapy

In the absence of treatment delays due to adverse event(s), treatment will continue until one of the following criteria applies:

- Disease progression
- Intercurrent illness that prevents further administration of treatment
- Unacceptable adverse event(s)
- Subject decides to withdraw study consent
- General or specific changes in the subject's condition render the subject unacceptable for further treatment in the judgment of the Investigator.

Note: In the event the criteria for the final analysis are met, and there are subjects who have not yet been discontinued from study treatment, they will continue to receive therapy beyond the date the criteria for the study final analysis are met and until one of the above criteria applies.

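### Section 5.5 ends survival follow-up when the final-analysis criteria are reached, so with short PFS it can stop before the planned one-year update

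*Combined protocol and SAP*

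**What the plan says.** Section 13.3.1 plans two analyses after the primary one. The first: "An updated analysis will be conducted after all enrolled participants have been on study for at least one year". The second is the final analysis, to be done "after the PFS censoring rate reduces to 20% or after all subjects have been on study for at least 3 years, whichever occurs first". The 3-year limb carries its own minimum follow-up. The 20% limb carries none.

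Section 5.5 (Subsequent Therapy and Survival Status) provides for long-term contact about every 6 months "until death or lost to follow-up, or until the criteria defined for the final analysis (Section 13.3.1) are reached". If the criteria are met while anyone is still taking nintedanib, "subjects in follow up will continue to be followed until all subjects have discontinued study treatment and completed the safety monitoring period". Section 7.3 provides for the same situation: such subjects stay on treatment, and "they will continue to receive therapy beyond the date the criteria for the study final analysis are met".

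Other provisions bear on the point but are permissive. Section 5.5 adds: "Long-term follow-up clinical information may also be obtained through chart reviews". Section 14.1 lets the sponsor-investigator set a cut-off date. Section 5.4.2 says: "Subjects may be completely withdrawn from the study by the Investigator if criteria for long-term follow-up described in Section 5.5 are met", and "Withdrawn subjects are considered to be off-study".

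**The concern.** Section 5.5 links the end of survival follow-up to the criteria being reached, not to the final analysis being carried out. Holding the final report back therefore does not keep follow-up open. The only extension that 5.5 prescribes lasts while someone is on drug or in safety monitoring. Because treatment stops at progression (5.2, 7.3), short PFS brings the 20% limb forward and shortens that extension too.

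No sentence keeps survival follow-up open to the update's one-year mark. At stake is OS for late enrollees, who could be censored before one year although the update is defined by everyone having reached it.

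**Working it through.** **Inputs from the documents.** N = 39 (13.1); accrual 48 months (4.1); scans every two 28-day cycles, that is every 56 days (5.5); treatment to progression (5.2, 7.3); safety period 30 days after last dose (11.4.1); PFS censored at the last scan before any new anti-cancer therapy (13.1.3).

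**Assumed, because the documents give no value for this population.** Median PFS 2.7, 4, 6 and 8 months. The first is the single-agent lung figure in 2.2.2: 11.6 weeks × 7 / 30.44 = 2.7 months. Also assumed: uniform accrual, exponential PFS, the share of subjects who never contribute a PFS event, and post-progression survival.

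**Events needed.** 7/39 = 17.9% and 8/39 = 20.5%, so at most 7 may be censored and 39 − 7 = 32 events are needed. If 8 or more are permanently censored, the 20% limb can never be met and the 3-year limb governs.

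**Hand check.** Follow-up closes before the update only if everyone is off drug by about 12 − 1 = 11 months after the last first dose. With subjects spaced 48/39 = 1.23 months apart and scan delay ignored, that probability is the product over k = 0 to 38 of [1 − 2^(−(11 + 1.23k)/m)], where m is median PFS. It gives 80%, 45%, 10% and 1.5% for m = 2.7, 4, 6 and 8. Progression is found only at the next scan, so the true values are somewhat lower.

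**Simulation** (20,000 trials per scenario). The criteria are met at the later of the 32nd detected PFS event and the last subject's first scan, and at most 36 months after the last first dose. Survival follow-up ends then if nobody is on drug, otherwise 30 days after the last subject stops. The update falls 12 months after the last first dose.

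| Median PFS (months) | 2.7 | 4 | 6 | 8 |
|---|---|---|---|---|
| Criteria met before update, no permanent censoring | 100% | 100% | 99.9% | 96% |
| Follow-up ends before update, none | 72% | 35% | 7% | 1% |
| Same, 10% permanently censored | 69% | 34% | 7% | 1% |
| Same, 20% permanently censored | 34% | 17% | 3% | 1% |

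The first two rows differ because of the on-drug extension. At a 12-month median the gap is about 0%.

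**Stopping drug before progression** (assumed exponential, mean 12 months; 31% to 53% stop early). The result depends on how many of those who stop begin new therapy before progression, because 13.1.3 then censors their PFS:

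| Early stoppers who start new therapy first | 2.7 | 4 | 6 | 8 |
|---|---|---|---|---|
| None | 90% | 74% | 52% | 36% |
| Half | 69% | 38% | 10% | 2% |
| Three quarters | at most 28% | lower | lower | about 0% |

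The reason is arithmetic. At the 8-month median, 39 × 0.53 × 0.5 = 10.3 subjects are censored on average, more than the 7 allowed.

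**Effect on OS** (treated to progression, no permanent censoring; assumed median PFS/OS in months):

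| PFS/OS | 2.7/8.7 | 4/12 | 4/18 | 6/24 |
|---|---|---|---|---|
| OS censored at update, under 5.5 | 9.4% | 13.3% | 27.4% | 36.8% |
| OS censored, uninterrupted | 5.8% | 11.7% | 25.6% | 36.5% |
| Mean deaths missed, all trials | 1.4 | 0.6 | 0.7 | 0.1 |
| Mean deaths missed, trials with a gap | 2.0 | 1.8 | 2.0 | 1.6 |

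The rows agree: (9.4% − 5.8%) × 39 = 1.4 deaths. At 2.7/8.7 the estimated median OS averages 8.82 months (SD 1.37) with the early cut and 8.78 (SD 1.35) without; the SD of 12-month OS is 7.7 against 7.6 points. At 6/24 the median is 24.38 (SD 4.41) against 24.36 (SD 4.39).

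**The case against.** The strongest reply is that nothing of consequence is lost. OS is a secondary, descriptive Kaplan-Meier estimate, the cut-off is driven by the calendar and brings no material bias in this model, and precision hardly moves. That stands, and it keeps the point minor.

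The second reply is that the plan already copes: the on-drug extension, chart review, a sponsor-set cut-off, and the commitment to an update with a year on study for all. The extension is in the model and the gap remains at short PFS. The next two are options only. A sponsor reading 5.5 and 13.3.1 together might well keep following everyone, but 5.5 as written does not require it.

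The third is that short PFS is borrowed from lung cancer, while 2.1 describes a disease spectrum that includes less aggressive, mucin-rich tumors. This is fair. At a median of 6 months or more, with treatment to progression, the gap is 7% or less.

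A reader might also infer more than the documents support:
- *That the final analysis must precede the update.* Both are to be done after their conditions are met, so the sponsor may hold the final report. The order of reports is not the defect.
- *That early stopping of drug always widens the gap.* It does so only if few of those who stop start new therapy before progression.
- *That tumor assessment stops too.* Under 5.5 and note f of the study calendar, scans after stopping for reasons other than progression run to progression or new therapy and are not tied to the final-analysis criteria.
- *That subjects will be withdrawn at the trigger.* Section 5.4.2 only permits it, and its wording is unclear.

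**Conclusion.** The point holds as a minor one. A stated rule in 5.5 can close survival follow-up before an analysis that 13.3.1 plans. Under treatment to progression the risk is substantial at median PFS of about 4 months or less (35% to 72% with no permanent censoring), small at 6 months and negligible at 8. About 20% permanent PFS censoring roughly halves it.

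These frequencies rest on assumed exponential PFS, uniform 48-month accrual and assumed censoring and stopping patterns, so they show a range and do not predict this trial. The damage is confined to the OS estimate at the update. The primary test has its own timing in 13.3.1, based on best overall response, and is unaffected.

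**What to change.** Change one sentence in 5.5: continue long-term survival follow-up until the later of (a) the 13.3.1 final-analysis criteria being reached and (b) 12 months after the last subject's first dose, keeping the existing extension while anyone is on drug or in safety monitoring. Twelve months is the plan's own update point, and by construction follow-up can then no longer end before it.

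The cost is extra survival follow-up averaging 3.2, 1.2, 0.2 and 0.02 months at median PFS of 2.7, 4, 6 and 8 months if subjects are treated to progression. It is longer if many stop drug early, up to about 7.5 months in the most extreme case examined (mean stopping time 4 months, none of those who stop censored for PFS). It uses the existing 6-monthly phone, clinic or chart contacts.

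The 13.3.1 timing rule need not change. Adding a 12-month floor there would often put the updated and final analyses on the same date (96% to 100% of simulated trials at medians 2.7 to 8 with no permanent censoring) and would delay the final report by a median of about 8 to 10 months where the trigger is early. That is a trade-off for the sponsor and is not needed to close this gap.
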